Section 5.2, Exclusion Criteria	In exclusion criterion #12, HBV-DNA testing description was added, and the HCV definition was updated.	Refer to rationale for change in Section 8.3.8.
	Moved QuantiFERON-TB Gold testing guidance from criterion #13 to corresponding Section 8.3.6.	To clarify study entry guidance and initial TB retesting.
	In exclusion criterion #19, Table 1 Prohibited Medications, the 5-drug half-lives period of phototherapy was deleted.	Phototherapy does not have a half-life.
	A footnote was added to Table 1 Prohibited Medications to indicate that medications are prohibited until the last dose of study intervention is administered.	Updated to align with Sections 6.5 and 8.1.5.2.
Section 6.3.1, Intervention Assignment	Modified text to indicate that participants will alternate between placebo and MK-6194.	Refer to Section 4.1 rationale regarding study intervention.
Section 6.3.2, Stratification	Descriptions of stratification factors were expanded.	Updated to address investigator/site feedback.
Section 7.1, Discontinuation of Study Intervention	Added criterion for discontinuation if HBV-DNA is \geq LLOQ.	Refer to rationale for change in Section 8.3.8.
Section 8.1.1.3, Consent for PK/PD/Biomarker Subpopulation	Text added to indicate PK/PD/Biomarker consent will be collected at selected sites.	PK/PD/Biomarker testing is limited to selected sites.
Section 8.1.11, Participant Blinding/Unblinding	Added treatment unblinding guidance.	Inadvertently omitted during original protocol creation.
Section 8.1.13, PK/PD/Biomarker Subpopulation	Modified the text to indicate that enrollment for the PK/PD/Biomarker sampling will be at least 15 participants per arm.	Refer to rationale for change in Section 4.1.

Section Number and Name	Description of Change	Brief Rationale
Section 8.2.1, PROs	Added PROs timing and training information.	To harmonize with other sections of the protocol.
Section 8.3.2, Vital signs	HR and BP will be assessed similarly.	Corrected to avoid confusion.
	Added collection of vital signs timing exception.	Corrected a protocol inconsistency.
Section 8.3.6, TB Testing	Added TB testing guidance.	Refer for change in Section 5.2 regarding TB testing.
Section 8.3.7, Chest X-ray	Added the focus of chest x-rays is to identify TB.	Added as additional investigator guidance.
Section 8.10.2, Double-Blind Treatment Period	Added clarification regarding PROs administration.	Refer to rationale for change in Section 8.2.1.

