4.4 Beginning and End-of-Study Definition

The overall study begins when the first participant (or their legally acceptable representative) provides documented informed consent. The overall study ends when the last participant completes the last study-related contact, withdraws consent, or is lost to follow-up (Section 7.3). For purposes of analysis and reporting, the overall study ends when the Sponsor receives the last laboratory test result or at the time of final contact with the last participant, whichever comes last.

If the study includes countries in the European Economic Area (EEA), the local start of the study in the EEA is defined as First Site Ready (FSR) in any Member State.

See Appendix 7 for country-specific requirements.

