17. Has a concurrent clinically significant disease or clinically relevant laboratory abnormalities, or a history of any illness or medical condition that, in the opinion of the investigator, might confound the results of the study or poses an additional risk to the participant by their participation in the study

Prior/Concomitant Therapy

18. Has had an inadequate response (as evaluated by a dermatologist or local physician specialist equivalent) to previous treatment with a JAKi after an appropriate treatment duration (eg, ≥ 12 weeks)

Note: Up to approximately 50% of participants with previous JAKi use study wide are eligible if the following criteria are met:

- Response to previous treatment with a JAKi after an appropriate treatment duration (ie, ≥ 12 weeks)
- History of previous JAKi use for < 12 weeks regardless of response status

For these participants, the last dose of the JAKi should be ≥ 4 weeks prior to Randomization.

19. Has received prohibited medications within the specified timeframes prior to Randomization ([Table 1](#)). These medications are also prohibited during the study:

Table 1 Prohibited Medications

Medication Category	Prohibited Period Prior to Randomization and Any Time During the Study ^a
Biologics and Targeted Immunosuppressive Therapies	
Recombinant IL-2 IL-2 muteins/analogs Immune checkpoint inhibitors (ie, PD-1 inhibitors, PD-L1 inhibitors, CTLA-4 inhibitors, etc). See Appendix 8 Permanent skin bleaching agents	Any time
T-cell depleting therapies (eg, alemtuzumab, antithymocyte globulin)	12 months
B-cell depleting therapies (eg, rituximab, ocrelizumab)	6 months

Medication Category	Prohibited Period Prior to Randomization and Any Time During the Study^a
Biologics with immunosuppressive potential. See Appendix 8 for examples of biologics Note: Non-immunosuppressive biologics may be used after discussion with the study Clinical Director	3 months or 5 half-lives (whichever is longer)
JAK inhibitors (JAK1, JAK2, JAK3) (including selective inhibition) TYK2 inhibitors PDE4 inhibitors S1P modulators See Appendix 8 for examples of these medications	4 weeks
Medications Used to Treat Vitiligo	
Any drug inducing photosensitivity such as including, but not limited to certain antibiotics (eg, tetracyclines), certain NSAIDs	2 weeks

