Antioxidants (eg, polypodium leucotomas, superoxide dismutase, alpha-lipoic acid, Ginko Biloba)	No newly initiated 3 month prior to Randomization, and the dose should remain stable during the study duration
Other topical treatments or any procedures (eg, needling) that could affect vitiligo	4 weeks (or 5-drug half-lives)
Systemic or topical non-biologic immunomodulators/immunosuppressants (eg, corticosteroids, calcineurin inhibitors, tacrolimus/pimecrolimus)	4 weeks for systemic, and 2 weeks for topical
Any kind of phototherapy (eg, UV/UVB phototherapy, PUVA therapy, tanning beds, laser therapy)	4 weeks
Any other prescription or over-the-counter medication, traditional Chinese medicine, herbal supplement, or other therapy used to treat vitiligo	4 weeks
Other Therapies	
Any investigational drug	4 weeks or 5 half-lives of the investigational drug (whichever is longer)
Live vaccines Note: JYNNEOS for prevention of smallpox and mpox, (also known as monkeypox disease) is allowed. JYNNEOS is a live, non-replicating vaccine. See Appendix 8 for examples of live and non-live vaccines.	4 weeks (or longer if required locally)
CTLA-4=cytotoxic T-lymphocyte-associated protein 4; JAK=Janus kinase; IL-2=interleukin 2; NSAIDs= nonsteroidal anti-inflammatory drugs; PD-1= programmed cell death protein 1; PDE4= phosphodiesterase-4 enzyme; PD-L 1= programmed cell death ligand 1; PUVA=psoralen and ultraviolet rays A; S1P= sphingosine 1 phosphate; TYK2= tyrosine kinase 2; UV/UVB=ultraviolet/ultraviolet rays B. ^a Medication use is prohibited until the last dose of study intervention is administered (study completion or early discontinuation).	

See Appendix 7 for country-specific requirements.

Prior/Concurrent Clinical Study Experience

20. Has participated in another investigational clinical study within 4 weeks (see [Table 1](#) for prohibited period) prior to Randomization

Diagnostic Assessments

21. Has Screening laboratory test results within the following parameters:

- Hemoglobin <8.5 g/dL
- WBC < $3.5 \times 10^3/\mu\text{L}$
- Absolute neutrophil count < $1.5 \times 10^3/\mu\text{L}$
- Absolute lymphocyte count < $0.5 \times 10^3/\mu\text{L}$
- Absolute eosinophil count >1000 cells/ μL
- Absolute platelet count < $100 \times 10^3/\mu\text{L}$
- >2.0 X ULN of any of the following: ALT, AST, ALP, or >ULN total bilirubin (1.5 X ULN total bilirubin if known Gilbert's syndrome)
- eGFR $\leq 30 \text{ mL/min/1.73 m}^2$, based on the MDRD equation

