5.3 Lifestyle Considerations

Blood Donation

Study participants should be instructed not to donate blood or blood products during the study.

Sun or Light Exposure

Study participants should be instructed to avoid prolonged exposure to the sun (ie, without sufficient SPF protection or in sun conditions where skin could be impacted). The use of tanning booths, sun lamps, or other ultraviolet light sources are prohibited during the study.

Makeup/Tattooing/False Eyelashes/Self-Tanning

- Permanent and semipermanent makeup is not permitted. Cosmetic makeup is permitted; however, must be removed for clinical assessments at all study visits.
- Tattooing, including procedures such as microblading and micropigmentation, are not permitted during the study. Existing tattoos are allowed as long as the assessment of vitiligo is not impaired per investigator clinical judgment.

- False eyelashes are permitted; however, should be removed for clinical assessments at all study visits.
- Self-tanning and dyes are not permitted during the study.
- Laser treatment: intense pulsed light therapy and any laser treatment, including for hair removal and skin pigmentation, is not permitted during the study.
- Needling is not permitted during the study.
- Existing beards are allowed as long as the assessment of vitiligo is not impaired per investigator clinical judgment.

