6.3.3 Blinding

A double-blinding technique with in-house blinding will be used. MK-6194 and placebo will be packaged identically so that blind is maintained.

Clinical site personnel, participants, and most Sponsor personnel will remain blinded for the duration of the study (ie, through Week 54). Only selected Sponsor personnel involved in performing and reviewing the results of the Week 24 analyses will be unblinded at the time of the Week 24 database lock.

See Section 8.1.11 for the description of unblinding if a medical emergency occurs during the study.

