6.5 Concomitant Therapy

Prohibited Concomitant Medications

Medications or vaccinations specifically prohibited in the exclusion criteria are also prohibited during the study. Please refer to [Table 1](#) (in Section 5.2) for medications which are prohibited during the study until the last dose of study intervention. Live vaccines, except for JYNNEOS, are prohibited during the study until 6 weeks after the last dose of study intervention. See Appendix 8 for examples of live vaccines and Appendix 7 for country-specific requirements.

Any prescription or over-the-counter medication, traditional Chinese medicine, herbal supplement, or other therapy used to treat vitiligo (or could affect vitiligo) are prohibited during the study to avoid confounding of results.

If there is a clinical indication for any medications or vaccinations specifically prohibited, discontinuation from study intervention may be required. The investigator should discuss any questions regarding this with the Sponsor Clinical Director. The final decision on any supportive therapy or vaccination rests with the investigator and/or the participant's primary physician. However, the decision to continue the participant on study intervention requires the mutual agreement of the investigator, the Sponsor, and the participant.

Any medication or vaccine (including over-the-counter or prescription medicines, vitamins, and/or herbal supplements or other specific categories of interest) that the participant is receiving at the time of enrollment or receives during the study must be recorded along with:

- Reason for use
- Dates of administration including start and end dates
- Dosage information including dose, route, and frequency

The Sponsor Clinical Director should be contacted if there are any questions regarding concomitant or prior therapy.

Note: It is the responsibility of the investigator to ensure participants with concomitant medical conditions are treated according to local guidelines/standard of care.

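### The ban on vitiligo-active therapy ends at the last dose (about Week 50) in four places, two weeks before the final Week 52 efficacy ratings, while two other places set no last-dose limit (minor)

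*Protocol*

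**What the plan says.** Four places in the protocol tie the end of the ban to dosing.

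- Section 5.2, Table 1, footnote a: "Medication use is prohibited until the last dose of study intervention is administered (study completion or early discontinuation". The footnote hangs on a column header that reads "Prohibited Period Prior to Randomization and Any Time During the Study".
- Section 6.5 paragraph 1 refers to Table 1 "for medications which are prohibited during the study until the last dose of study intervention".
- Section 8.1.5.2 sets the same limit for prohibited concomitant medications, therapies and products.
- Appendix 8 sets it for the drug classes it covers, including JAK, TYK2 and PDE4 inhibitors.

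Two places have no last-dose limit.

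- Section 6.5 paragraph 2 says that therapies "used to treat vitiligo (or could affect vitiligo) are prohibited during the study to avoid confounding of results".
- Section 5.3 says: "The use of tanning booths, sun lamps, or other ultraviolet light sources are prohibited during the study". It rules out laser treatment and needling on the same basis.

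The extension schedule (section 1.3.2) puts the last dose at Week 50 and the closing efficacy ratings at Week 52. Section 8.10.5 lifts the ban for participants who stop study intervention early, and it also ends their efficacy data collection.

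**The concern.** The two sets of rules cover overlapping therapies. Section 6.5 paragraph 2 closely repeats a Table 1 row on other vitiligo treatments. Tanning beds, laser and needling are in both Table 1 and section 5.3. The same therapy can therefore carry two end dates, and adjacent paragraphs of section 6.5 differ.

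The difference spans a scored visit. Early discontinuers are rated at the time they stop and have no efficacy data collected after the ban lifts. Completers are the only group that the last-dose rule releases and then scores. That sits badly with the reason section 6.5 gives for the ban, which is to keep results free of confounding.

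What is at stake is how the last reading of the extension is interpreted. Participants who began on placebo start active drug at Week 24, so Week 52 is their only efficacy reading after more than 24 weeks on drug. For the original MK-6194 arms it is the last reading on longer treatment.

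**Working it through.** **Timeline.** The schedule's day numbers follow Day = 7 × week + 1. This reproduces the printed days: Week 24 = 169, Week 48 = 337, Week 52 = 365.

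- Last dose, Week 50: 7 × 50 + 1 = Day 351.
- Final ratings, Week 52: Day 365.
- Nominal interval: 365 − 351 = 14 days, which agrees with the two weeks stated in section 4.1.

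**Range of the interval.** The protocol gives the last dose only approximately, and the dosing-interval text is redacted, so these ranges are assumptions.

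| Assumption | Shortest | Longest |
|---|---|---|
| Last dose on Day 351, Week 52 visit ±7 days | 358 − 351 = 7 days | 372 − 351 = 21 days |
| As above, last dose also shifted ±3 days | 358 − 354 = 4 days | 372 − 348 = 24 days |

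**Readings exposed** (section 1.3.2).

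- F-VASI in the extension: Weeks 28, 32, 36, 44 and 52, so 1 of 5.
- T-VASI, patient-reported outcomes and global ratings: Weeks 36 and 52, so 1 of 2.
- Unredacted instruments at Week 52: VitiQoL, VNS, PGI-S, PGIC/M, CGI-S, CGI-C, F-VASI and T-VASI, which makes eight.

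**Time on active drug for participants first assigned to placebo.** Week 52 gives 52 − 24 = 28 weeks. The previous F-VASI gives 44 − 24 = 20 weeks. The previous T-VASI, patient-reported and global ratings give 36 − 24 = 12 weeks.

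**Week 24.** Participants who complete the double-blind period continue dosing in the extension, and the Week 24 procedures precede the Week 24 dose. The last-dose rule therefore still bans these therapies when the primary and secondary endpoints are rated.

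**Effect of the fix.** Ending the ban when the Week 52 assessments are complete reduces the uncovered interval from a nominal 14 days to 0. No sample size, power or alpha figure changes.

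**The case against.** The best reply is that the last dose was the intended meaning throughout. Footnote a qualifies the column header, section 6.5 paragraph 1 joins the two phrases, and section 8.1.5.2 and Appendix 8 agree. The summary of changes explains the edit: "A footnote was added to Table 1 Prohibited Medications to indicate that medications are prohibited until the last dose of study intervention is administered". The row that section 6.5 paragraph 2 echoes is itself under that footnote. On this view paragraph 2 merely omits a limit already given, and the end date is the sponsor's choice.

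Much of this stands: the last dose probably was the intended rule for medications. It does not remove the point. If it was intended, it still releases completers before a scored visit, against the purpose stated in section 6.5. The bracketed words in footnote a do not help, because they can name the two ways dosing ends or a later end of participation. Section 5.3 is not under the footnote. It covers only light sources, laser, needling and cosmetic items, however, so for drugs the unlimited rule rests on section 6.5 paragraph 2 alone.

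A reader might go further and infer that the protocol fixes a later end date for the ban. The documents do not support that. Section 6.3.3 says site staff, participants and most sponsor personnel "will remain blinded for the duration of the study (ie, through Week 54", which would be Day 379, but that sentence is about blinding and is only indirect evidence. Section 4.4 says "The overall study ends when the last participant completes the last study-related contact". That defines the end of the whole trial, not of one participant's obligations, and should not be used here.

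The reply is also right that the impact is limited. SAP section 3.5.2 makes the extension analyses descriptive, with no comparison between groups. The protocol treats 12 weeks or more as an appropriate JAK inhibitor course, so about two weeks of new therapy may change VASI little. Concomitant medication is reviewed at Week 52, recorded with dates (section 6.5) and summarised (SAP section 3.5.4), so use would be visible, though not prevented.

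**Conclusion.** The point holds as a minor one. The explicit last-dose rule lets extension completers start vitiligo-active therapy a nominal 14 days before their last efficacy rating, and two other places state the ban without that limit. No text says which rule applies to completers between Week 50 and Week 52.

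Only the descriptive Week 52 data are exposed. It would be wrong to infer that the Week 24 primary or secondary analysis is compromised: the ban is in force at Week 24 for participants who continue into the extension as section 4.1 describes, and early discontinuers have no later efficacy data. It would also be wrong to say that Week 52 will be confounded. The documents do not say how many participants would start such therapy or how far it would move the ratings, and the effect is probably small. The 14 days assume a last dose on Day 351 and a visit on Day 365.

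**What to change.** Use one end point everywhere: *until the Week 52 efficacy assessments are completed, or until early discontinuation of study intervention*. Put it in Table 1 footnote a, section 6.5 paragraphs 1 and 2, section 8.1.5.2, Appendix 8, and the light, laser and needling items of section 5.3. Section 6.5 paragraph 2 and section 5.3 must be included; otherwise two end points remain.

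Apply it to every Table 1 row except live vaccines, which keep their rule of 6 weeks after the last dose and any longer country requirement. Sites then need not judge which drugs could affect vitiligo. Leave section 8.10.5 as it is.

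No SAP change is required. If wanted, Week 52 readings taken after new vitiligo therapy can be flagged from the medication dates already recorded.

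The cost is a wording change at the next amendment, with the usual regulatory and ethics review and no new data. The downside is about two more weeks of restriction for extension completers, which section 6.5 paragraph 2, read literally, already imposes for vitiligo therapy.

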5.3 Lifestyle Considerations

Blood Donation

Study participants should be instructed not to donate blood or blood products during the study.

Sun or Light Exposure

Study participants should be instructed to avoid prolonged exposure to the sun (ie, without sufficient SPF protection or in sun conditions where skin could be impacted). The use of tanning booths, sun lamps, or other ultraviolet light sources are prohibited during the study.

Makeup/Tattooing/False Eyelashes/Self-Tanning

- Permanent and semipermanent makeup is not permitted. Cosmetic makeup is permitted; however, must be removed for clinical assessments at all study visits.
- Tattooing, including procedures such as microblading and micropigmentation, are not permitted during the study. Existing tattoos are allowed as long as the assessment of vitiligo is not impaired per investigator clinical judgment.

- False eyelashes are permitted; however, should be removed for clinical assessments at all study visits.
- Self-tanning and dyes are not permitted during the study.
- Laser treatment: intense pulsed light therapy and any laser treatment, including for hair removal and skin pigmentation, is not permitted during the study.
- Needling is not permitted during the study.
- Existing beards are allowed as long as the assessment of vitiligo is not impaired per investigator clinical judgment.

5.4 Screen Failures

Screen failures are defined as participants who consent to participate in the clinical study, but are not subsequently randomized in the study. A minimal set of screen-failure information is required to ensure transparent reporting of screen-failure participants to meet the CONSORT publishing requirements and to respond to queries from regulatory authorities. Minimal information includes demography, screen-failure details, eligibility criteria, and any AEs or SAEs meeting reporting requirements as outlined in the data entry guidelines.

Rescreening is allowed once per participant (Section 8.1.6 and Section 8.10.1).

5.5 Participant Replacement Strategy

A participant who discontinues from study intervention or withdraws from the study will not be replaced.

6 STUDY INTERVENTION

Study intervention is defined as any investigational intervention(s), marketed product(s), placebo, or medical device(s) intended to be administered to a study participant according to the study protocol.

Clinical supplies study intervention(s) provided by the Sponsor will be packaged to support enrollment as required. Clinical supplies will be affixed with a clinical label in accordance with regulatory requirements.

6.1 Study Intervention(s) Administered

The study intervention(s) to be used in this study are outlined in [Table 2](#).

Table 2 Study Interventions

Arm Name	Arm Type	Intervention Name	Intervention Type	Dose Formulation	Unit Dose Strength(s)	Dosage Level(s)	Route of Administration	Treatment Period	Use	IMP or NIMP/AxMP	Sourcing
MK-6194 Q2W	Experimental	MK-6194	Biological/Vaccine	Injection, Solution	3 mg	3 mg	SC	Double-Blind Treatment and Blinded Extension Periods	Test Product	IMP	Provided centrally by Sponsor
MK-6194 Q4W	Experimental	MK-6194	Biological/Vaccine	Injection, Solution	3 mg	3 mg	SC	Double-Blind Treatment and Blinded Extension Periods	Test Product	IMP	Provided centrally by Sponsor
MK-6194 Q4W	Experimental	Placebo	Biological/Vaccine	Injection, Solution	0 mg	0 mg	SC	Double-Blind Treatment and Blinded Extension Periods	Placebo	IMP	Provided centrally by Sponsor
Placebo Q2W	Placebo Comparator	Placebo	Biological/Vaccine	Injection, Solution	0 mg	0 mg	SC	Double-Blind Treatment Period	Placebo	IMP	Provided centrally by Sponsor

EEA= European Economic Area; IMP= investigational medicinal product; NIMP/AxMP= noninvestigational/auxiliary medicinal product; Q2W= every 2 weeks; Q4W= every 4 weeks; SC= subcutaneous.

The classification of IMP and NIMP/AxMP in this table is based on guidance issued by the European Commission and applies to countries in the EEA. Country differences with respect to the definition/classification of IMP and NIMP/AxMP may exist. In these circumstances, local legislation is followed.

Note: To maintain the blind for MK-6194 Q4W, alternating placebo will be administered between the MK-6194 doses. Participants randomized to the placebo arm Q2W during the Double-Blind Treatment Period will be rerandomized to MK-6194 Q2W or MK-6194 Q4W during the Blinded Extension Period.

All supplies indicated in [Table 2](#) will be provided per the “Sourcing” column depending on local country operational requirements. If local sourcing, every attempt should be made to source these supplies from a single lot/batch number where possible (eg, not applicable in the case where multiple lots or batches may be required due to the length of the study, etc).

Refer to Section 8.1.9 for details regarding administration of the study intervention.

